**South Texas Early Prevention Studies PreK**

**Study Design and Protocol**

**September 28, 2018**

## **Study Design and Participants**

The STEPS-PreK4 was a CRT where preschools, embedded within elementary schools, were the unit of randomization, intervention, and analysis. The study was designed for two years of intervention (pre-kinder to kindergarten) and four data collection periods (fall 2018, spring 2019, fall 2019, and spring 2020). Due to the COVID-19 pandemic the study was stopped prematurely and only results from the first three periods will be presented.

The two school districts where the study was conducted are located along the Texas-Mexico border in the county of Hidalgo. These school districts were selected because of the high poverty and health risk-factors levels. The preschools have two grade levels with children 3 and 4 years of age. The present study targeted preschools with children 4 years of age. Demographics of the two school districts were similar, 99% Hispanic, 92% economically disadvantaged, and 42% identified as English as a second language.

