### **Sample Size Calculation**

The sample size for the primary endpoint, obesity prevalence, assumed a 5% obesity rate decrease in the intervention compared to control group, a SD of 1.4, an intra-cluster correlation coefficient of 0.01, 70% response rate, and an attrition rate of 16 percent. [source: LJ ISD, PSJA ISD] A total of 28 preschools (clusters) with a mean cluster size of 49 children per school was estimated to detect the effect size with 80% power at a significant level of  $\alpha = 0.05$ . The calculated sample size was enough for a difference of at least 4.5 laps between treatments (secondary outcome) and the statistical power was 82% for alpha 0.05 with sample size of 40 children per cluster.

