**South Texas Early Prevention Studies PreK**

**Study Design and Protocol**

**September 28, 2018**

## **Statistical Analyses**

Summary statistics are presented as means (standard deviations; S.D.), and frequencies (percentages) to describe the treatment groups, and p-values adjusted by random factors. The primary aim of this report was to assess the longitudinal effect of the BN CSHP on the CRF of children as compared to a control group. The CRF was measured by the number of laps in the PACER fitness test. The counts of laps were positively skewed and assumed to follow a Poisson probability distribution. The linear fixed predictors of the average number of laps were time (continuous variable consisting of the periods of data collection), treatment effect (discrete factor with control group as the reference level), and their interaction (the nested district-level, school-level, and classroom-level to account for random intercepts).

A generalized linear mixed model (GLMM) with a natural logarithm link and a Poisson probability distribution was fitted to the data using the R package lme4, version 1.1-27.1. Upon detecting a significant overdispersion, a GLMM with a negative binomial distribution was used instead to assess the unadjusted and adjusted effect of the intervention and to obtain 95% confidence intervals (CI).

The models were adjusted for covariates sex, age, body mass index (BMI), education level of caretaker who responded to the demographic survey, household income to poverty ratio (IPR), time watching T.V., time playing with electronic devices, hours of sleep at night, and time exercising outside school. The interactions between period and treatment by BMI, sex, and age were also included in the full model. As suggested by Brown all continuous variables were transformed to a unit-scale and used the Bound Optimization BY Quadratic Approximation optimizer in the lme4 package to ensure convergence. The analysis was performed in R version 4.1.0 [R Core Team, 2013].

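### The laps model does not link a child's own records, so leaving that depends on earlier laps, and does so differently by arm, would bias the treatment-by-time estimate

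*SAP*

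**What the plan says.** SAP, Statistical Analyses, gives the aim as to "assess the longitudinal effect of the BN CSHP on the CRF of children as compared to a control group", with laps as the measure. The fixed terms are "time (continuous variable consisting of the periods of data collection"), treatment and their interaction. The random part is given only as "their interaction (the nested district-level, school-level, and classroom-level to account for random intercepts"). After overdispersion was found, "a GLMM with a negative binomial distribution was used instead to assess the unadjusted and adjusted effect of the intervention". On covariates: "The models were adjusted for covariates sex, age, body mass index (BMI), education level of caretaker who responded to the demographic survey", followed by income, screen time, sleep and exercise items. Fall 2018 laps are not on that list.

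Protocol, Study Design and Participants, says "only results from the first three periods will be presented", so each child has at most three lap counts: fall 2018, spring 2019 and fall 2019.

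Protocol, Sample Size Calculation, assumes "70% response rate, and an attrition rate of 16 percent" when sizing the obesity endpoint. Attrition is not split by arm and not tied to a period. Neither document defines a lap analysis set, states a missing-data assumption, or describes imputation or a sensitivity analysis for missing laps.

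**The concern.** A likelihood-based mixed model tolerates dropout that depends on earlier outcomes because it links a child's earlier and later values. The stated model has no such link. Given district, school, classroom, arm, period and covariates, it treats a child's three counts as independent. A leaver's fall 2018 count then says something about the classroom but nothing about that child's missing 2019 counts.

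Suppose low-lap children leave more often in one arm. That arm's later mean rises because of who is still measured, and the treatment-by-time term absorbs the rise as if it were an effect. As described, the plan has no analysis that would reveal or correct this in the result it calls its primary aim.

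**Working it through.** **The plan's own figures.** 28 schools × 49 children = 1,372; 16% of that is about 220 children, if 49 is the number enrolled. The stated power cannot be reproduced, because control obesity prevalence and the SD of laps are not given. It does not bear on this point.

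**Mechanism.** With period t = 0, 1, 2 and arm A, the stated model is log μ = β0 + β1·t + β2·A + β3·t·A + district + school + classroom. The false ratio at fall 2019 is exp(2·β3) when the true β3 is 0. With no child term, the likelihood of a child's counts is a product over periods given the area effects, so an observed count carries no child-specific information about a missing one. Adding a child intercept and integrating over it restores the link.

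**Simulation 1: planned type of model, no true effect.** From the documents: 28 schools × 49, three periods, about 16% lost overall, and district, school and classroom intercepts. Assumed: mean 10 laps at the start, child SD 0.5 on the log scale, growth 0.2 per period, negative binomial size 10, and a slope of leaving of 1 per SD of log laps where lap-related. There were 100 runs per row, no covariates, and a Monte Carlo SE of about 0.002 on β3.

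| Leaving by fall 2019, control / intervention | β3, no child term | exp(2·β3) | Rejection at 5% | Ratio with child intercept |
|---|---|---|---|---|
| 8% / 24%, unrelated to laps | 0.0024 | 1.005 | 0% | 1.006 |
| 16% / 16%, same lap-dependence | 0.0024 | 1.005 | 2% | 1.004 |
| 12% / 20%, low-lap children leave | 0.0138 | 1.028 | 2% | 1.005 |
| 8% / 24%, low-lap children leave | 0.0247 | 1.051 | 6% | 1.004 |
| 16% / 16%, lap-related in intervention arm only | 0.0269 | 1.055 | 10% | 1.006 |
| 16% / 16%, opposite direction by arm | 0.0560 | 1.119 | 64% | 1.004 |

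The first two rows are within Monte Carlo error of no bias. So is every child-intercept result (at most about 1.7 Monte Carlo SE from zero), with rejection of 3 to 8%.

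In laps, the fall 2019 mean is about 10 × exp(0.4) × exp(0.5²/2) = 10 × 1.492 × 1.133 ≈ 17. The false differences are then 17 × 0.028 ≈ 0.5, 17 × 0.051 ≈ 0.9, 17 × 0.055 ≈ 0.9 and 17 × 0.119 ≈ 2.0 laps.

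**Simulation 2: different assumptions, selection placed in the control arm.** Mean 12 laps, within-child correlation 0.5, 16% lost in each arm. Moderate pattern: 28% of the lowest quarter of starting laps leave against 12% of the rest (0.25 × 0.28 + 0.75 × 0.12 = 0.16). The lowest quarter then makes up 0.25 × 0.72 / 0.84 = 21.4% of the control children still measured. Strong pattern: 40% against 8% (0.25 × 0.40 + 0.75 × 0.08 = 0.16), which leaves 0.25 × 0.60 / 0.84 = 17.9%.

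False ratios from 600 runs of a negative binomial GLM were 0.983 and 0.964 (−0.36 and −0.63 lap), and 0.920 (−1.46 laps) with opposite selection. The same pattern in both arms gave 1.000. Predicting missing fall 2019 laps from fall 2018 laps gave 0.998 to 1.001 throughout. A mixed model with school and classroom intercepts (40 runs each, not run for opposite selection) agreed: 0.983 and 0.967.

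**Dependence on within-child correlation.** In a Gaussian log-scale version of Simulation 1's lap-related patterns that differ by arm, the bias in β3 ran from 0.007 to 0.063 per period as the correlation went from 0.3 to 0.7. That is a ratio of 1.01 to 1.13. With a child intercept it was about zero.

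**The case against.** Several objections stand and limit the point.

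- A reader might infer that different leaving rates are enough to bias the result. They are not: 8% against 24%, unrelated to laps, gave none. Nor does any lap-related leaving suffice, since the same dependence at the same rate in both arms cancels.
- A reader might also infer a raised false-positive rate in general. With school-clustered standard errors, the Simulation 2 GLM rejected in 7.5%, 12.8% and 44.0% of trials for moderate, strong and opposite selection, but that is not the planned test. The mixed model rejected in 2.5% and 0% for the first two (40 runs each), and in 2 to 10% of the moderate Simulation 1 cases. Without the child term its standard error for β3 is too large (about 0.025 against an empirical 0.020), which masks the bias in the test. Inflation is clear only with opposite selection.
- The documents do not say that only available records are used. That is inferred from their silence and from how the named model behaves without imputation.
- The 16% is an obesity planning figure. Nothing in the documents indicates lap-related or arm-specific leaving, and opposite selection is an extreme case.
- The adjusted model includes sex, age, BMI and activity items, so selection explained by these is partly handled. The simulations leave them out. The unadjusted estimate has no such help.

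The point that one extra model term removes the bias seen here is also right, and it shapes the fix. None of this restores the missing link between a child's records.

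**Conclusion.** The point holds as a conditional one. As written, the laps model gives a biased treatment-by-time estimate when leaving depends on laps and that dependence, or its rate, differs by arm. With about 16% lost by fall 2019, the false ratio is off by about 2 to 6% in moderate patterns (0.4 to 0.9 lap, or 8 to 21% of the 4.5-lap target). It is off by about 8 to 12% with opposite selection (1.5 to 2 laps, about a third to just under half of the target). The direction depends on which arm loses its low-lap children.

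The defect is bias in the estimate and its interval. The documents do not support saying that this trial's result is biased, or that its test size is generally inflated. The sizes rest on assumed leaving patterns, lap means and spread, and within-child correlation, none of which the documents give.

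**What to change.** In SAP, Statistical Analyses:

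1. Define the lap analysis set as all children measured in fall 2018, in the arm of their fall 2018 school.
2. Add a child random intercept, nested in classroom, to the negative binomial GLMM used for the main laps analysis. State which classroom defines the nesting, since the study runs from pre-kindergarten into kindergarten.
3. State the assumption this makes: leaving may depend on observed laps and modelled covariates, but not on unseen laps.
4. As a sensitivity analysis, multiply impute missing laps separately by arm from the child's other laps, school, classroom and all analysis-model covariates including BMI. Shift the imputed laps in one arm until the conclusion changes, to cover leaving that depends on unseen laps.
5. Report leaving by arm and by fall 2018 laps, so that readers can judge whether the condition for bias is met.

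The cost is SAP wording, more model specification and some convergence work: in Simulation 1, 85 to 95 of 100 child-intercept fits gave usable standard errors. No new data are needed.

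### The longitudinal PACER model has no child random intercept and no school-by-time term, so the standard error of treatment-by-time is not valid as specified

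*SAP*

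**What the plan says.** The SAP (Statistical Analyses) sets the target: "The primary aim of this report was to assess the longitudinal effect of the BN CSHP on the CRF of children". The outcome is the number of PACER laps. The fixed effects are "time (continuous variable consisting of the periods of data collection), treatment effect (discrete factor with control group as the reference level), and their interaction". Directly after this, in a parenthesis, come the random effects: "the nested district-level, school-level, and classroom-level to account for random intercepts". The model starts as Poisson, and the SAP then reports a change: "Upon detecting a significant overdispersion, a GLMM with a negative binomial distribution was used instead".

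The Protocol (Study Design and Participants) states that "preschools, embedded within elementary schools, were the unit of randomization, intervention, and analysis". It describes "two years of intervention (pre-kinder to kindergarten) and four data collection periods", of which the first three periods are analysed. Its Sample Size Calculation assumes "an intra-cluster correlation coefficient of 0.01, 70% response rate, and an attrition rate of 16 percent", with 28 schools and, for the lap outcome, 40 children per school.

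Neither document mentions a child-level random effect, a within-child correlation structure, a robust variance or a random school-by-time term.

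**The concern.** Following children from pre-kinder to kindergarten, with an allowance for attrition, implies a cohort with up to three PACER results per child. This is inferred; the documents do not say it outright. Under the listed random effects, two results from one child are no more alike than results from two classmates.

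The negative binomial dispersion does not repair this. It adds independent extra variation to each record, so stable differences between children count as fresh noise at every period.

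A second gap bears on the same coefficient. Schools were randomised, but the model lets them differ only by a constant. If schools change at different rates for reasons unrelated to treatment, that variation belongs in the SE of treatment-by-time, and the model leaves it out.

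The two gaps push the SE in opposite directions. What is at stake is the confidence interval and test for the coefficient that answers the stated aim.

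**Working it through.** **No plan figure to reproduce.** The documents give no SE or power for treatment-by-time. The stated 82% power concerns a difference of 4.5 laps between treatments, and no standard deviation is identified for laps.

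**Inputs from the documents.** 28 schools, m = 40 children per school, 3 periods; random intercepts as listed.

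**Assumptions (not in the documents).** Log-scale approximation with within-school variance set to 1: child share ρ and residual share 1 − ρ. ρ is 0.3, 0.5 or 0.7. The school-by-period variance share is s. School variance is 0.01; classroom variance is 0.01 or 0.02.

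**Closed form, stable classrooms, complete data.** Code the periods −1, 0, 1. A school's slope is half the difference between its last and first means.

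- True variance of a school's slope: [(1 − ρ)/m + s]/2, because the child intercept cancels.
- Variance under the plan's model: about (1/m)/2, because child variation is treated as independent noise.
- Model SE / true SE, plan: 1/√(1 − ρ + m·s).
- Model SE / true SE, child intercept only: √[(1 − ρ)/(1 − ρ + m·s)].
- The plan's SE is right only when m·s = ρ, that is s = ρ/m.

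**Results with s = 0.**

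| ρ | closed form | GLS with sandwich variance | size of a 5% test, 2Φ(−1.96/√(1 − ρ)) |
|---|---|---|---|
| 0.3 | 1/√0.7 = 1.20 | 1.19 | 1.9% |
| 0.5 | 1/√0.5 = 1.41 | 1.40 | 0.6% |
| 0.7 | 1/√0.3 = 1.83 | 1.80 | 0.03% |

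If classrooms are re-formed at kindergarten (two per school), the GLS ratios are 1.16/1.33/1.59 at classroom variance 0.01 and 1.14/1.28/1.48 at 0.02. With 49 children per school, 16% attrition and stable classrooms they are 1.17/1.35/1.65.

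**Break-even.** s = ρ/40 = 0.0075/0.0125/0.0175 (GLS 0.0074/0.0123/0.0172). With classrooms re-formed it is about 0.009/0.015/0.021. Above these values the plan's SE is too small.

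**Results with s > 0, ρ = 0.5.**

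- s = 0.02: 1/√(0.5 + 0.8) = 0.88, size 8.6%.
- s = 0.05: 1/√(0.5 + 2.0) = 0.63, size 21.5%.
- Child intercept only, s = 0.02: √(0.5/1.3) = 0.62.

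**Negative binomial simulation.** No true effect, ρ = 0.5, mean about 10 laps, stable classrooms, district intercept omitted; 300 datasets per plan-model row and 200 per row with a child term.

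| Model fitted | s | mean model SE / empirical SE | ratio | rejected at 5% |
|---|---|---|---|---|
| Plan | 0 | 0.0238 / 0.0186 | 1.28 | 0 of 300 |
| Plan | 0.02 | 0.0240 / 0.0271 | 0.89 | 8.3% |
| Plan | 0.05 | 0.0242 / 0.0392 | 0.62 | 22.3% |
| Child only | 0 | 0.0172 / 0.0170 | 1.01 | 4.5% |
| Child only | 0.02 | 0.0176 / 0.0284 | 0.62 | 22.5% |
| Child + school-by-period | 0.02 | 0.0267 / 0.0287 | 0.93 | 6.0% |

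The Monte Carlo SE of the ratios is 0.03 to 0.06.

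**Power, for illustration only.** A test with 82% power at the correct SE would have power Φ(2.875 − 1.96 × ratio) with the plan's SE. At s = 0 this is 70%/54%/24% with complete data and 72%/59%/36% with 16% attrition.

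**Treatment main effect.** The ratio is 1.00 at mid-time. If time is coded from the first period it is 1.04 to 1.12, with no school-by-time variance. The problem lies mainly in treatment-by-time.

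**The case against.** **A missing child term alone is conservative.** This is true: it costs power and widens intervals but creates no false positives. At ρ = 0 there is no error at all, and the documents give no correlation. Even so, repeat fitness results from one child can hardly be expected to be uncorrelated, and an SE 1.2 to 1.8 times too large is still wrong.

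**The false-positive case rests on assumed school drift.** This is also true. The plan's only intra-cluster correlation, 0.01, is for obesity at school level. If all of it were school-by-period variance for laps, the ratio would be 1/√(1 − ρ + 0.4) = 0.95/1.05/1.20, with size at most 6.2%. At half of it, the ratio is 1/√(1 − ρ + 0.2) = 1.05/1.20/1.41, conservative throughout. The settings s = 0.02 and 0.05 are therefore illustrations and not estimates. But no figure is given for laps, and break-even lies close to 0.01, so neither direction can be excluded.

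**The larger figures are the least secure.** Attrition trims the ratios slightly. At a mean of 10 laps and a log-scale child SD of 0.4, Poisson noise of about 0.1 caps the correlation near 0.16/0.26 = 0.62, so the 0.7 column needs greater child variation or higher counts. The simulated ratio at s = 0 (1.28) is below the linear 1.40. Re-forming classrooms lowers the linear ratio to 1.33 but gave 1.38 in simulation, a difference not fully explained. Covariates may absorb some child variation in the adjusted model. These points change the size and leave the fault in place.

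**It may be a reporting gap.** The parenthesis is unclear, and a child term may have been fitted. If so, one sentence settles that half; the school-by-time term is still absent.

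**Conclusion.** The concern holds and needs correcting before the treatment-by-time interval is relied on. As written, the model omits both the correlation between a child's repeat results and random school-by-time variation, so its SE for the longitudinal effect is not valid.

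With only the child term missing, the SE is roughly 1.2 to 1.8 times too large across correlations of 0.3 to 0.7. Once the school-by-period share passes about 0.007 to 0.02, it becomes too small and false positives rise above 5%. The net direction is unknown.

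This rests on the inference that the same children were retested and on assumed variances, since the plan gives none for laps. If each period had sampled different children, the child-level part would vanish; nothing in the documents suggests that.

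**What to change.** State whether the same children were retested and list every random effect in full. Then do one of the following for both the unadjusted and the adjusted model:

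- Keep the planned intercepts and add a child random intercept together with a school-by-time term (a school-by-period intercept or a school random slope on time), for example `(1|district) + (1|school) + (1|classroom) + (1|child) + (1|school:period)`. Label classroom as the room attended at that period, so that it is crossed with child.
- Or use a school-level cluster-robust variance with a small-sample correction for 28 clusters.

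Do not add the child intercept alone. It removes the conservatism and leaves school drift uncovered: at s = 0.005 the closed form gives √[(1 − ρ)/(1 − ρ + 0.2)] = 0.88/0.85/0.77, or a test size of about 8% to 13%.

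Re-check overdispersion afterwards, since the child term will take up part of it. With only two districts, the district variance is barely estimable; this is already so in the plan, and the example formula with district included was not simulated.

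The cost is two terms in the lme4 formula, longer run time, possible convergence work, and an interval that may widen if school-by-time variance is present. No new data are required.

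### Classroom is undefined after the move to kindergarten and no child intercept is listed, so the interval for the treatment-by-time slope on laps is unreliable

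*SAP*

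**What the plan says.** Protocol, Study Design and Participants: the trial was planned for "two years of intervention (pre-kinder to kindergarten) and four data collection periods (fall 2018, spring 2019, fall 2019, and spring 2020"). After the early stop, "only results from the first three periods will be presented". The analysed data are therefore two pre-K measurements and one kindergarten measurement. In the same section, "preschools, embedded within elementary schools, were the unit of randomization, intervention, and analysis".

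SAP, Statistical Analyses: "The primary aim of this report was to assess the longitudinal effect of the BN CSHP on the CRF of children". The fixed effects are time as a continuous variable, treatment and their interaction. The random part is given as "the nested district-level, school-level, and classroom-level to account for random intercepts". After overdispersion was found, "a GLMM with a negative binomial distribution was used instead to assess the unadjusted and adjusted effect of the intervention".

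Neither document says which classroom is attached to a fall 2019 record, how kindergarten classes were formed from pre-K classes, or how large the classroom and child variances of laps are. No child-level or crossed random effect is listed.

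The SAP makes fitness the primary aim of this report. The protocol's Sample Size Calculation section calls laps the secondary outcome.

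**The concern.** The last period has the most leverage on a linear slope, and it is the only one measured after the children changed grade. The classroom identifier can be read in two ways:

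- **Pre-K class carried forward.** The model treats classroom variation as cancelling from each child's change, and it has no term for the clustering that the kindergarten class adds in fall 2019.
- **Current class at each period.** The class clustering is described correctly, but repeated laps from one child are treated as independent once class is accounted for.

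At stake are the width of the interval for the treatment-by-time effect and, in some circumstances, the slope itself. Two analysts who both follow the SAP could report different results from the same data.

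**Working it through.** **The plan's own figure.** The only figure for laps is 82% power for 4.5 laps with 40 children per cluster. It cannot be reproduced because no SD of laps is given. With 14 schools per arm (assumed) and ICC 0.01 it implies an SD of about 22 laps. It does not bear on this point.

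**Inputs.** From the protocol: 28 schools and about 49 children per school (48 used here). Assumed: 14 v 14; three classes of 16; children redistributed evenly over three kindergarten classes, each with a new class effect; times 0, 1, 2; no dropout; no school-by-period variance; total variance 1 on the log-lap scale. School share is s = 0.01, taken from the protocol's ICC, which is stated for obesity and not for laps. Class share c is 0.005 to 0.05, child share k is 0 to 0.5, and residual e = 1 − s − c − k. R is model SE divided by true SE, and type I error is 2Φ(−1.96R).

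**Reading 1: pre-K class carried forward.** The slope is (period 3 − period 1)/2.

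- True variance per school: ¼(2c/3 + 2e/48).
- Model variance per school: ¼(2v/48), where v is the fitted residual variance.
- Hence R = √[v/(16c + e)].
- Without a child term, v = (48/47)[1 − s − (4/9 + 1/27)c − k/16 − e/48].

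Two corners of the grid:

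- c = 0.05, k = 0, e = 0.94: v = 0.9665 and R = √(0.9665/1.74) = 0.745, so type I error is 14.4%.
- c = 0.005, k = 0.5, e = 0.485: v = 0.9664 and R = √(0.9664/0.565) = 1.31, so type I error is 1.0%.

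| Class share | k = 0 | k = 0.3 | k = 0.5 |
|---|---|---|---|
| 0.005 | 5.9% | 2.7% | 1.0% |
| 0.01 | 6.8% | 3.5% | 1.6% |
| 0.03 | 10.7% | 7.2% | 4.8% |
| 0.05 | 14.4% | 11.1% | 8.7% |

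**Reading 2: current class, no child term.** Put a = c/3 and b = e/48, with a′ and b′ the same quantities from the fitted variances. The weights are (−0.5 + d, −2d, 0.5 + d) with d = −a′/(2a′ + 6b′).

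- Model variance per school: 2a′(0.5 + d)² + b′(0.5 + 6d²).
- True variance per school: the same expression with a and b. The child effect cancels.

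The fitted variances come from the large-sample maximum-likelihood solution:

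- c = 0.05, k = 0.3: fitted class 0.0526, residual 0.9332. Variances are 0.01646 (model) and 0.01266 (true), so R = 1.14 and type I error is 2.5%.
- c = 0.005, k = 0.5: fitted class 0.0113, residual 0.9727. Variances are 0.01191 and 0.00584, so R = 1.43 and type I error is 0.5%.
- k = 0: R = 1.00 at every class share.

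**Period weights.** Reading 1 gives (−0.50, 0, 0.50). Reading 2 at c = 0.05, k = 0 has a′ = 0.01667, b′ = 0.01958 and d = −0.11, giving (−0.61, 0.22, 0.39).

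- Log treatment differences of 0, 0.10, 0.05: slopes are 0.50 × 0.05 = 0.025 and 0.22 × 0.10 + 0.39 × 0.05 = 0.0415.
- Linear differences of 0, 0.05, 0.10: both slopes are 0.05 (0.50 × 0.10, and 0.22 × 0.05 + 0.39 × 0.10).

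**Adding a child intercept (k = 0.3 or 0.5).**

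- To reading 1: R falls to between 0.95 and 0.62. For example, at c = 0.05, k = 0.3 the fitted v is 0.6733, so R = √(0.6733/1.44) = 0.68 and type I error is 18%.
- To reading 2, crossed with class: R = 1.00 in every case.

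**The case against.** A reader might infer that a nested classroom intercept assumes each child keeps one classroom, so that the model is wrong as written. The documents do not support that. With no child term, it is records and not children that are nested in classrooms, and a class identifier specific to the school year nests validly within school. Nor do they show that any interval was computed wrongly, because they do not say which label was used.

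Other points against:

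- **Direction and size rest on assumptions.** Carried-forward type I error falls on both sides of 5%. The only ICC in the documents is 0.01. At class shares up to 0.01 the range is about 1% to 7%, and much of it is conservative. This stands, and it is why no single figure is offered.
- **The too-wide intervals come from the missing child term, not from classroom nesting.** This also stands. With the current-class label, adding the child intercept repairs the width.
- **Classes may have moved up together.** If the class effect itself persisted, it would cancel from the change and carrying the label forward would be right on that point. If the groups stayed together but the kindergarten class effect was new, the error is much the same: R is 0.74 and 0.81 at class share 0.05 with child shares 0 and 0.3 (school share 0.02).
- **Different slopes need a treatment difference that is not linear in period.** Correct. The labels alone do not change the target.
- **The model is negative binomial and the protocol expects 16% attrition.** The linear, balanced calculation is only a guide to size.

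What remains is that laps from the same child are very likely to be correlated, and then neither reading reliably gives correct error bars.

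**Conclusion.** The point holds as a specification gap with consequences for inference. The SAP leaves classroom undefined across a grade change that the protocol makes explicit, and it lists no child intercept.

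- **Pre-K class carried forward, classes re-formed:** type I error about 1% to 14% over the whole grid, and about 1% to 7% at class shares up to 0.01.
- **Current class:** standard error about 14% to 43% too large at child shares of 0.3 to 0.5 (type I error about 0.5% to 2.5%), and correct only if repeat laps from one child are uncorrelated.
- **Slope:** period weights depend on the label, but the estimand changes only if the treatment difference is not linear in period.

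The class and child variances, class layout and 14 v 14 split are assumptions, and school-by-period variance and dropout are left out. The documents do not establish that a reported interval is too narrow or too wide. They establish that the plan does not secure a correct one.

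**What to change.** Define classroom as the class attended at each measurement, with an identifier specific to the school year and nested in school, and add a child random intercept crossed with it. Make both changes together: a child intercept with the pre-K class carried forward would make the standard error too small.

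Add two sensitivity analyses:

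1. Period as a factor, which shows whether the treatment difference is linear in period.
2. A comparison of school-level changes between arms by t test, with degrees of freedom equal to the number of analysed schools minus 2 (26 if all 28 are analysed). This needs no classroom label, though it makes no allowance for district.

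The cost is a class identifier for each school year and a change in the random-effects specification, with no new measurement. The model becomes slightly more complex and may have convergence problems, and intervals may widen or narrow.

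### With 28 schools planned, the SAP names no small-sample method for its 95% intervals; a nominal 5% test of a between-school contrast would run at about 6.0% to 6.5% at the planned ICC

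*SAP*

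**What the plan says.** The Protocol (Study Design and Participants) states that "preschools, embedded within elementary schools, were the unit of randomization, intervention, and analysis". Its Sample Size Calculation gives "A total of 28 preschools (clusters) with a mean cluster size of 49 children per school", an ICC of 0.01, a 70% response rate, 16% attrition and an alpha of 0.05. Neither document states the allocation ratio or the randomisation scheme.

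The SAP (Statistical Analyses) models PACER laps on time, treatment and their interaction, with nested random intercepts for district, school and classroom. The Poisson model gives way to a negative binomial one if overdispersion is found, and that model is used "to assess the unadjusted and adjusted effect of the intervention and to obtain 95% confidence intervals (CI"). The section names the package version, the optimizer and the R version. It does not say whether the intervals are Wald, profile or bootstrap. It names no t or F reference, denominator degrees of freedom, variance correction or permutation test.

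**The concern.** With 28 randomised units, the information on a between-school contrast is limited by the number of schools, however many children are measured. A likelihood fit with default intervals can then err in two ways:

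- A normal (or chi-square) reference replaces t on about 26 df.
- Maximum likelihood divides the between-school sum of squares by 28 rather than 26, so it understates that variance by a factor of about 26/28.

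When the school variance is not estimated at zero, both errors make intervals too short. At stake is whether the stated 95% coverage is delivered for treatment contrasts that rest on schools.

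**Working it through.** **The plan's own figure.** The figure at issue is the nominal alpha of 0.05. The 80% power statement cannot be reproduced, because the control obesity rate is not given; nothing below depends on it.

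**Inputs.** From the Protocol: 28 schools, 49 children per school for the obesity endpoint, 40 per cluster for laps, ICC 0.01. If 49 is the number before losses, the number analysed is 49 × 0.70 × 0.84 = 28.8, about 29. Assumed: 14 schools per arm, two-sided tests (to match a 95% interval), a normal outcome model, and intervals from the likelihood fit with no correction. Degrees of freedom: 28 − 2 = 26.

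**Closed form for a between-school contrast, school variance not estimated at zero.**

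| Interval | Calculation | True size |
|---|---|---|
| Normal reference, unbiased variance | P(\|t26\| > 1.960) | 6.1% |
| Profile / likelihood ratio | t² > 26 × (exp(3.841/28) − 1) = 3.82, so P(\|t26\| > 1.955) | 6.1% |
| Normal reference, ML variance (Wald) | P(\|t26\| > 1.960 × √(26/28)) = P(\|t26\| > 1.889) | 7.0% |

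Spending one more degree of freedom on district (25 df) gives 6.1% to 7.6% across the three rows. With 20 schools instead of 28 the range is 6.6% to 7.9%.

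**Simulation at the planned ICC.** At a small ICC the estimated school variance is sometimes zero, and the test then falls back on a pooled variance with many more degrees of freedom. A balanced normal random-intercept model with 28 schools and no effect, fitted by ML with truncation at zero and tested against 1.96, gives:

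| ICC | 29 per school | 40 per school | 49 per school |
|---|---|---|---|
| 0 | 4.5% | 4.5% | 4.5% |
| 0.01 (planned) | 6.0% | 6.3% | 6.5% |
| 0.05 (assumed) | 7.0% | 7.0% | 7.0% |

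At ICC 0.01 the variance estimate is zero in about 29%, 21% and 15% of trials respectively, which is why the size stays below 7%.

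**What a t reference alone does.** The t(26) critical value is 2.056. Applied to the ML variance, the size is P(\|t26\| > 2.056 × √(26/28)) = P(\|t26\| > 1.981) = 5.8%. At ICC 0.01 with 40 children per school the simulated size is 5.1%, helped by truncation.

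**Interval width.** From the t quantile: 2.056/1.960 = 1.049. With the ML bias also removed: 1.049 × √(28/26) = 1.088.

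**The time-by-treatment term.** With random intercepts only, the school intercept cancels and the interaction is tested within schools. Simulated size under a normal model with 28 schools and three periods:

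- No school variation in trend and no within-child correlation: about 5%.
- School-slope variance of 0.5% of the residual variance (assumed): 8% to 10%.
- Within-child correlation of 0.3 or 0.5 (assumed), no school slopes: 1.9% or 0.6%. The listed random effects include none for the child.
- Correlation of 0.5 together with that slope variance: 3.8% to 4.5%.

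**The case against.** The strongest reply is that the SAP's aim is a longitudinal effect, carried by the time-by-treatment interaction. As modelled, that term draws on within-school change, so neither t(26) nor the 26/28 factor governs it. This stands. A reader might infer that the trial's main longitudinal result has a 6% to 7% false-positive rate; the documents do not support that, because the figure belongs to between-school contrasts.

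A reader might also infer that the error always favours a positive finding. It does not. The between-school test is slightly conservative at an ICC of zero, and the interaction test can be strongly conservative if repeated measures on the same child are correlated and not modelled.

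Other limits also stand:

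- The interval type is inferred from the likelihood fit and the absence of any correction. Wald and profile intervals both exceed 5% in the closed form, but the 7% end needs Wald with ML variance.
- The 7% end also needs an ICC above the only one in the Protocol.
- The 28 schools are the planned number, sized for obesity; the number analysed is not given.
- No negative binomial or three-level model was simulated.

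The reply does not show that the planned inference is safe. For the interaction, the documents leave even the direction of the error open.

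**Conclusion.** The point holds in limited form. For a between-school contrast such as the treatment term, uncorrected likelihood intervals with 28 schools give a true size of about 6.0% to 6.5% at the planned ICC, and about 7% at assumed ICCs of roughly 0.03 and above. That is an excess of about one to two percentage points. It rests on Wald or profile intervals, 14 schools per arm and a normal approximation to the count model.

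For the time-by-treatment interaction no single error rate can be stated. It depends on how much trends differ between schools and on within-child correlation, and the documents give neither. The severity is modest. It is still more than a missing detail, because inference at the level of the randomised school held close to 5% (4.5% to 5.7% by t on school-level slopes) in every interaction scenario simulated.

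**What to change.** State the interval method, and base inference for both the treatment and the time-by-treatment terms on the randomised school:

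- Add a school-by-period random effect, and refer the contrasts to t on the number of schools analysed minus 2 (26 if all 28 are analysed), or one fewer if district is fitted.
- Take the p-value from a permutation test that re-assigns schools under the actual randomisation scheme, or from a school-level analysis (for example of school slopes) with unbiased variance. The t reference alone does not remove the ML variance bias.
- Record the randomisation scheme, including any restriction by district, since the permutation test must follow it.

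The cost is an interval for a between-school contrast about 5% wider from the t quantile, or about 9% wider once the ML bias is also removed, with slightly less power. It needs no new data and a few lines of code.
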